Hypothesis 1: Compared to men assigned to an attention control condition, those exposed to the intervention will have lower levels of sexual risk behavior at a 3 and 6 month follow-up.

Hypothesis 2: Compared to men assigned to an attention control condition, those exposed to the intervention will have improved outcomes at 3 and 6 months, on theoretically derived mediators of sexual risk behavior, including interpersonal factors such as attitudes, self-efficacy, communication skills and perceived norms around safer behavior, as well as on factors such as increased individual and community empowerment and decreased HIV-related stigma.

Aim 2: To examine individual and contextual-level factors that explain variation in the efficacy of the intervention.

Hypothesis 3: Intervention impact will be moderated by individual and contextual level-factors such as higher perceived basic needs and housing instability, incarceration and substance use history, higher perceived racism, and traditional gender role norms and attitudes, such that intervention effects will be reduced among men with these risk factors.

Project Rationale:

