The sample size calculation is based on the expected percent of men engaging in high risk behavior after 6 months of follow-up, accounting for the intraclass correlation coefficient (ICC) and estimates of unprotected sex estimated from our pilot dataset of 105 participants from four barbershops. Unprotected sex, defined in this example as two or more sexual partners in the past three months plus at least one episode of unprotected vaginal or anal sex, was reported by 42% of our sample in a previous pilot study of the program. Assuming that 42% of the participants in the control group would engage in high risk behavior, an ICC of 0.03, and a minimum of 23 participants from each barbershop, the study has 80% power to detect an absolute reduction of 12% (relative reduction of 29%) in rates between the two groups with alpha=0.05, two-tailed and 15 barbershops for each intervention group (i.e., 30 clusters and 690 total participants). In order to achieve a sample size of 690 at the six-month follow-up, we estimate that we will need to recruit 875 men in order to account for a loss to follow-up as high as 20%.

Participants:

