Inclusion criteria include men age 18 or older who report two or more partners in the past six months, unprotected sex with a woman in the past six months, and identify as Black or African American. Exclusion criteria for participation include (1) having been in an HIV prevention research study in the last six months, (2) reporting a history in the past five years of injection drug use, (3) reporting a history in the past five years of having sex with other men, (4) reporting an HIV-positive serostatus, or (5) inability to understand spoken English. In order to ensure that our program meets the needs of a unique and understudied population, we have chosen to exclude men with an injection drug use history or who report same sex behavior, given that interventions have been developed for these populations and that the behavioral risk and determinants of risk are unique to these subpopulations. However, it is recognized that the very nature of being on the 'down low' would necessitate that some men who engage in same-sex relationships may not report this behavior and be included in the sample. Similarly, the stigmatized nature of injection drug use may be linked to underreporting during our screening and evaluation procedures. The risk in this scenario is that inclusion of men who for whom intervention messages are not tailored could dilute differences between the experimental and control group, but would not cause harm. We note that although we focus on men who identify as Black, some men will also report Latino ethnicity; these men will not be excluded from the study, as reflected in our planned enrollment table. However, given that our program is being completed in barbershops serving African American men, the vast majority of potential enrollees will be English-speaking. During a pilot test of the Barbershop Talk program, we found that of over 100 men who completed a screener, all were able to understand English. While this does not negate the fact that some non-English speaking men may have been less likely to agree to screener, it does speak to the project team's view that translation of all intervention sessions and evaluation measures would not be a worthwhile use of funds given that we are unlikely to be able to have a large enough number of non-English speakers in the sample to be able to draw conclusions about effectiveness in these sub-groups, and that the program was not tailored to what are likely the unique needs of men who are non-English speaking.

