Audio Computer-Assisted Self-Interview (ACASI) will be utilized to collect self-reported data at baseline (pre-intervention) and also at 3- and 6-month follow-up from the date of completion of the *Barbershop Talk* program. Respondents will listen to headphones and questions will be provided by a recorded voice stored in computer memory. The responses will be entered by pressing on the computer's touchscreen. A privacy screen will be utilized so that other barbershop customers cannot view responses, and headphones with disposable covers will be used so that respondents can listen to questions and answer options. Prior to baseline questions being administered, participants will complete a series of 'warm up' practice items. During our formative work, we piloted the recruitment, screening, consent and baseline procedures described in this project on 78 men and have found them to be feasible to implement, acceptable to barbershop personnel and clients, and a sound method for maintaining privacy and confidentiality. Additionally, at the 6-month interview participants will be asked to complete an additional set of questions to help identify the need for future programs. These final questions will be administered by a study staff in an interviewer led format. Questions 1-3 of the questionnaire pertain to existing knowledge about PrEP, and interest to receive more information about PrEP. In conjunction with these questions, study participants will be offered a PrEP brochure to increase their knowledge about HIV prevention. For question #4 of the interview a response card will be handed to study participants to facilitate the selection of their answers to that question. Participants will be reimbursed at \$20 for the baseline interview, \$30 for the three month follow-up assessment, and \$40 for the six month follow-up assessment, which is reasonable considering the length of the interview, and is in line with typical reimbursement levels for other HIV prevention program evaluations. The evaluation instruments will take approximately forty minutes to complete. All measures described in the following section have been selected based on their established reliability and validity in published HIV prevention studies and with adult African American populations.

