All measures included in the program evaluation have been selected based on their demonstrated reliability and validity in published research and in our own previous work in populations similar to the men in this study; we will pilot the instrument prior to administration. To examine hypothesis 1, our main outcome measure will be a composite measure of the proportion of respondents who report two or more partners in the last six months and report unprotected sex during this time. This outcome, which was reported by over 40% of our population in our formative work, is a more informative marker of risk than some other outcome measures used in HIV prevention trials (e.g., any unprotected vaginal or anal sex) in that it helps to differentiate persons engaging in unprotected sex in the context of a single monogamous partnership, versus those who are at higher risk for HIV infection. Other measures of risk will include (1) partner concurrency, (2) number of sexual partners, (3) condom use consistency, and HIV testing. Behaviors will be assessed over the previous three months. Of course, self-report measures of sexual risk behavior are prone to self-report bias as individuals are likely to inflate or deflate their responses based on factors such as gender norms around sexual behavior. However, we will engage in a number of activities to promote honesty in responses by (1) assuring men of the confidentiality of their responses and explain the system that will be used to ensure this, (2) stressing the importance of honest answers to the scientific integrity of the project and for informing community health, (3) and using ACASI. Responses on this measure will be correlated with measures such as sexual behavior and drug use to provide an estimate of the extent to which this bias contributes to scores. Often, clinic-based interventions are able to collect data on more 'hard' outcomes, such as STD rates. The ability to power these studies is based on the fact that participants at baseline typically have and are treated for STD, and that there are known and substantial risks for 'repeat' infections in the control group. In our study, however, it would neither be feasible to conduct STD testing, nor acceptable to do so in the context of a community-based study involving barbershops. As described in our second hypothesis, our intervention is designed to directly influence a set of theoretically derived variables, which in turn are expected to influence sexual risk. These mediating variables include intrapersonal variables such as condom use and HIV testing attitudes, self-efficacy, and subjective norms, as well as perceived skills in communication and negotiation skills around safer sex. These measures are typically ordinal in nature but analyzed as having interval level properties measures

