Statistical analysis will be performed by SAS version 9.2 (SAS Institute, Cary, NC). The primary analysis method for study outcomes to test the main effect of the *Barbershop Talk* intervention will be generalized estimating equations (GEE) models, accounting for the cluster randomization. A logit link function will be specified for binary outcomes (including the primary outcome of engaging in high risk behavior after 6 months of follow-up) while a identity link function will be specified for continuous outcomes. The effects of mediating and moderating variables will be tested by appropriate modeling methods (Jaccard, Turrissi et al. 1990; Shrout and Bolger 2002; MacKinnon, Fairchild et al. 2007). Generalized mixed effects models, treating barbershop as a random effect, will also be fit as sensitivity analyses. All statistical tests will be at the 5% (two-tailed) significance level for main effects and at the 10% (two-tailed) significance level for interactions, with no adjustment for multiple testing.

Timeline:

This is a five year study. We will spend the first six months of the study working with our community advisory board on issues of protocol development, on development and production of high quality graphics for the program, on training of study staff, on securing of IRB approvals for the work and recruiting barbershops. Given our past experience in the barbershops, and our recruitment goal of 875 men, we anticipate that we will enroll participants at the rate of 20-25 per month over a forty-two month period. This would carry our follow-up period through to month six of year five. In the last six months of year five, we will engage in data cleaning and analysis, and dissemination of research findings.

Human subjects considerations:

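### The SAP models condomless sex alone, which as written is neither the composite the protocol declares as its main outcome nor the one behind the 42% planning rate

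*Protocol*

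**What the plan says.** The protocol describes the outcome in several places, and the SAP describes it once.

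- **Protocol, Program Evaluation.** The main outcome for Hypothesis 1 is the proportion of men "who report two or more partners in the last six months and report unprotected sex during this time". Both components carry a six-month window. The section adds that this is an outcome "which was reported by over 40% of our population in our formative work". It prefers the composite to any unprotected sex because it separates men in one monogamous partnership from men at higher risk.
- **Same section**, straight after the list of other risk measures: "Behaviors will be assessed over the previous three months".
- **Protocol, Study design and sample size.** The outcome reported by 42% of the pilot sample is described "in this example as two or more sexual partners in the past three months plus at least one episode of unprotected vaginal or anal sex". Three months is attached to the partner count; the episode has no window of its own.
- **Protocol, Data analysis.** It refers to "the primary outcome of engaging in high risk behavior after 6 months of follow-up", which gives a visit and no recall period.
- **Protocol, Participants.** Men enter if they "report two or more partners in the past six months, unprotected sex with a woman in the past six months".
- **Protocol, timing.** Hypothesis 1 states that "those exposed to the intervention will have lower levels of sexual risk behavior at a 3 and 6 month follow-up", and assessments fall at "3- and 6-month follow-up from the date of completion" of the program.
- **SAP.** A logistic mixed model takes the six-month value of condomless sex as outcome, with barbershop as a random effect and baseline condom use and covariates as fixed effects. Covariates were kept if associated with baseline condomless sex or unbalanced between arms. Number of partners, a composite and a recall period are not mentioned.

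**The concern.** A primary result should answer the question the trial declared and was sized for. Here the protocol gives two composites with different windows, and the SAP then names an outcome that appears to be neither. The missing partner component matters most, because it is the feature by which the protocol justifies its choice. A man with one steady partner and no condom use does not count under either protocol composite, but he does count under condomless sex alone.

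A reader of the SAP result cannot tell what period it covers, how it relates to the 42% rate, or whether the change of components was deliberate.

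**Working it through.** **1. The definitions side by side**

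| Place | Partner component | Unprotected sex | Recall window |
|---|---|---|---|
| Protocol, Program Evaluation (main outcome) | at least 2 | yes | six months for both |
| Protocol, Program Evaluation (later sentence) | not specific | not specific | three months |
| Protocol, Study design and sample size | at least 2 | at least 1 episode | three months for partners; none stated for the episode |
| Protocol, Data analysis | not stated | not stated | none stated |
| SAP | none | condomless sex | none stated |

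The three-month sentence may cover only the other risk measures. If so, the six-month main outcome conflicts with the sizing definition. If it covers everything, Program Evaluation contradicts itself. Neither reading reconciles the documents.

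**2. The plan's own figures**

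- Pilot count: 0.42 × 105 = 44.1, about 44 men.
- Relative reduction: 0.12 / 0.42 = 28.6%, the stated 29%.
- Recruitment: 690 / 0.80 = 862.5, so 863 men; the planned 875 covers this.
- Power: the design effect is 1 + (23 − 1) × 0.03 = 1.66, and effective n per arm is 345 / 1.66 = 207.8. A two-sided pooled test of 42% against 30% then has 72.3% power, against the stated 80%. That shortfall is a separate matter and nothing here rests on it.

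**3. What the 42% says about the other outcomes**

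Every pilot man counted in the 42% had at least one unprotected episode.

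- For condomless sex alone over the same window as that episode, the pilot rate is therefore at least 42%.
- For the six-month composite, it is also at least 42%, provided the episode fell within six months.

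In both cases 42% is a floor for the pilot sample and not an estimate. The documents give no upper value, and they do not say whether the pilot used the trial's entry rule.

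**4. Does a higher control rate change the sizing?**

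The control rates above 42% are assumptions. The 30 clusters of 23 men and the ICC of 0.03 are held fixed.

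| Control rate | Power, 12-point reduction | Power, 28.6% relative reduction |
|---|---|---|
| 42% | 72% | 72% |
| 50% | 69% | 84% |
| 60% | 69% | 94% |
| 70% | 72% | 99% |

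Power for a 12-point reduction hardly moves. For a constant relative reduction it rises. The difficulty is what the result means, and a loss of power has not been shown.

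**5. Which window was probably used?**

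Entry requires at least two partners and unprotected sex within six months. A six-month baseline item would therefore be close to constant, whether it measured the composite or condomless sex alone. The SAP screened covariates against baseline condomless sex and adjusted for baseline condom use, and both steps need variation between men. This makes a six-month window unlikely. It is not proof, because screening and baseline answers can differ.

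**6. Overlap with the period before the program**

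Pre-program months in a window of w months at visit month v = max(0, w − v).

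| Visit | Six-month window | Three-month window |
|---|---|---|
| Month 3 | 3 of 6 (50%) | 0 of 3 |
| Month 6 | 0 of 6 | 0 of 3 |

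**The case against.** **The SAP label may be shorthand.** The sample size section itself uses unprotected sex as its name for a composite that includes partners, so condomless sex in the SAP might mean the same. This cannot be excluded. However, the SAP does not define the term, and its baseline covariate is described as condom use, which points to a condom item alone. If it is shorthand, one sentence in the SAP would settle the matter.

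**The sizing definition is only an example.** The protocol does present it that way, so it does not override the declared main outcome. It is still the definition that produced the planning rate.

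**The window conflict has limited consequences.** This stands. The SAP evidence points away from a six-month window. The SAP describes no month-3 model, so overlap at month 3 affects only a month-3 result for Hypothesis 1, and only if a six-month question was asked then.

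**Stronger readings that the documents do not support:**

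- *The month-6 comparison is biased.* There is no pre-program overlap at month 6 with either window, and the entry criteria apply equally to both arms.
- *The outcome was chosen after seeing the results.* The SAP is dated 8/16/18. The protocol's retention date (January 2022, five years after study end) puts the end near January 2017, some 18 to 19 months earlier. Together with the past tense, this shows a retrospective document. It does not show why or when the outcome was chosen.
- *The trial was made too small by the wrong rate.* The power table above does not bear this out.

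**Conclusion.** The point holds, and it should be fixed. The protocol declares a six-month composite and takes its planning rate from one with a three-month partner count. The SAP, read as written, models condomless sex with no partner component, no recall window and no explanation. Its result therefore tests neither the declared main outcome nor the one the trial was sized on, and the 42% rate cannot be carried over to it.

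Confidence is high for the textual conflict. The size of any effect on the month-6 estimate is unknown, because no document gives rates under the other definitions. The month-3 concern is secondary and doubly conditional: it needs a six-month question at that visit and a month-3 analysis. The verdict assumes that condomless sex in the SAP carries its ordinary meaning.

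**What to change.** In the SAP:

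1. State the components and recall window of the outcome actually collected and analysed, and of its baseline covariate.
2. Report at month 6 the composite of at least two partners plus unprotected sex, in both the Program Evaluation form and the sample size form, as far as the data allow. Use the same mixed model, with each composite's own baseline value as covariate where it varies.
3. Label condomless sex alone as a deviation from the protocol's main outcome, with the reason.
4. State that the 42% planning rate refers to the sample size definition only.
5. If a six-month question was asked at month 3, report that half its window precedes program completion, as a limitation of any month-3 result.

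Do not settle on one composite now. The analysis is retrospective, and picking either would be post hoc endpoint selection. Reporting every pre-stated form avoids that.

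The cost is a few sentences, one or two extra month-6 models and a disclosed deviation; no new data are needed.

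There are limits to what can be recovered. If only three-month questions were asked, the six-month partner count cannot be fully rebuilt from the two follow-up visits, because one partner reported at each may be the same person. If only six-month questions were asked, the three-month form is unavailable. A three-month window at month 6 also covers only months 3 to 6. Each of these should be stated where it applies.

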
Intervention implementation:

Interventionists will be centrally trained using a standardized protocol developed by the principal investigator regarding appropriate techniques of group facilitation. At each barbershop, the intervention will begin with the training of barbershop staff and owners. Barbers will be paid \$40 for participation in the training, to compensate them for time spent away from clients. We recognize that all barbers may not be willing to participate in the training, and will monitor this as part of our evaluation procedures. Once barbers are trained, we will begin recruitment of participants. Intervention activities will take place at various locations central to and within sites of recruitment. Because the intervention involves personal information shared in a group format, we cannot hold program activities when other customers are in the barbershop. For these weekend sessions, we will hold activities in the AAIUH or SUNY Downstate, or we will rent space at a restaurant or other centrally located space. Trained study staff will implement the intervention; intervention staff will be independent from evaluators for the program. Participants will be provided with a nominal provision of \$20.00 USD for attendance at the program; this will be provided to both intervention recipients and those in the attention control group. The decision to provide this amount was based on discussions with our study team; who felt that participants are giving their time to participate in a study protocol with no guarantees of improving their health, and that if the program is effective, the amount may be low enough to make implementation feasible with some additional fiscal support. The scheduling and completion of intervention sessions and study interviews will be logged by date, visit number, and completion status; this information will be used to track monthly and cumulative accession and accrual rates.

Control group:

Although a classic randomized control trial involves comparison of persons who receive versus who do not receive an intervention, this conceptualization of a control group can be viewed as an unfair use of resources among population members who have been traditionally underserved in research and who distrust the research paradigm based on historical abuses. From the academic perspective, some scientists also believe that control groups should be similar in terms of the amount and nature of time spent with participants in intervention and control groups in order to improve the internal validity of conclusions. In response to these concerns and in consultation with our team, we are including a time and attention control group. All

participants assigned to the group will be scheduled to receive a curriculum focused on prostate cancer detection. This curriculum has several key advantages. This intervention was developed by the Arthur Ashe Institute in order to address racial/ethnic disparities in prostate cancer mortality, was constructed based on input from the communities that are the focus of the *Barbershop Talk* program, was demonstrated to be feasible and acceptable to implement, and produced changes in knowledge and attitudes among men with similar sociodemographic characteristics as those in our study sample (Fraser, Brown et al. 2009).

Data management:

Evaluation assessments will take place via ACASI, with all other data forms (e.g., locator, enrollment, contact logs, and final interview questions) completed manually. For the linked baseline, 3, and 6 month assessments, we will assign each study participant a unique study identification number and their name and study ID number will be linked on a Locator Form (which will provide detailed contact information for follow-up, and will help reduce the of participants enrolling more than once), on an Enrollment Log (which will provide date and location of enrollment and scheduled interviews), on a Contact Log (which will document contacts of the client with data collection staff) and in the local data management system. Locator Forms, Enrollment Logs, signed Consent Forms, and Contact Logs will be kept in locked file cabinets in a locked office in SUNY DMC. Data transmission will be tracked and monitored by the project coordinator. ACASI interview data will be encrypted during the ACASI interview as information is captured and saved on the computer's hard drive, which will be transmitted to the project coordinator daily. Computer programs will be developed to check data completeness and consistency. Each system file will have its own system dictionary containing variable names, labels, valid code values and labels and missing data definitions. The SUNY IS Division performs nightly automated backups on a Digital Linear Tape system. In addition, once each month a complete backup tape is made for offsite storage. All data stored on the servers are password protected and encrypted.

Data analysis:

Statistical analysis will be performed by SAS version 9.2 (SAS Institute, Cary, NC). The primary analysis method for study outcomes to test the main effect of the *Barbershop Talk* intervention will be generalized estimating equations (GEE) models, accounting for the cluster randomization. A logit link function will be specified for binary outcomes (including the primary outcome of engaging in high risk behavior after 6 months of follow-up) while a identity link function will be specified for continuous outcomes. The effects of mediating and moderating variables will be tested by appropriate modeling methods (Jaccard, Turrissi et al. 1990; Shrout and Bolger 2002; MacKinnon, Fairchild et al. 2007). Generalized mixed effects models, treating barbershop as a random effect, will also be fit as sensitivity analyses. All statistical tests will be at the 5% (two-tailed) significance level for main effects and at the 10% (two-tailed) significance level for interactions, with no adjustment for multiple testing.

Timeline:

This is a five year study. We will spend the first six months of the study working with our community advisory board on issues of protocol development, on development and production of high quality graphics for the program, on training of study staff, on securing of IRB approvals for the work and recruiting barbershops. Given our past experience in the barbershops, and our recruitment goal of 875 men, we anticipate that we will enroll participants at the rate of 20-25 per month over a forty-two month period. This would carry our follow-up period through to month six of year five. In the last six months of year five, we will engage in data cleaning and analysis, and dissemination of research findings.

Human subjects considerations:

We are applying for a federal Certificate of Confidentiality for this study, and will submit an amendment when the Certificate is obtained. Some potential risks for studies involving reduction in HIV-transmission behaviors include possible mild psychological distress at reflecting upon and being asked questions related to sexual behavior and other potentially stigmatizing factors. This possible distress is likely to be experienced for only a brief duration, that is, during the interview or discussion. This risk is expected. To minimize the potential psychological risks for participants, we will ensure that a) study staff are fully trained to deal with emotional responses to difficult questions or issues that are brought up and b) that appropriate referrals for treatment with a social worker or some other mental health provider are available to the respondent should he or she require support following any phase of study participation. Interviewers will report to the Project Director and Principal

Investigator any instances in which participants experience psychological discomfort so that we can determine adverse event status. Additionally, there is some risk that during the brief risk assessment, other customers at the barbershop will be able to observe responses to the brief risk assessment that are being entered into the ACASI. To the extent possible, participants will complete the ACASI in a setting in which other customers will not be able to view these entries, and a privacy screen and headphones are used so that others cannot view information on the screen nor hear the questions being asked of the participant. If a private setting is not available at the time of the brief risk assessment, we will ask participants to sit with the computer screen away from other customers (e.g., in a corner). Another possible risk is that information discussed in the group setting of the intervention could be provided to others by another participant outside of the group session. If information is of a personal nature, then it could cause potential harm. We will work within groups to set parameters for participation, including the importance of keeping all group discussions confidential, and discussion of the fact that participants should not divulge information in group settings that could harm them if it was released outside of the study. Participants will be informed that they can refuse to discuss any issues that they feel uncomfortable discussing. If participants are injured by being in this study, emergency care will be available; however the participant's medical insurance will be billed. SUNY Downstate Medical Center and the Arthur Ashe Institute do not have a policy to pay participants if they are injured by being in the study.

All data will be collected specifically for research purposes, and no data collection will take place until all protocols are approved and while approval is active. All participants will be recruited within the barbershops identified and recruited by the program team. Individuals within barbershops who are eligible and who are willing to learn more about the study will meet with a member of the study staff who will review all aspects of the study goals, the extent of participation, risks and benefits, and will provide an explanation of how confidentiality will be ensured. To participate, clients must first provide informed consent for all aspects of study participation and sign an IRB-approved consent form. A signed copy of the IRB approved consent form will be provided to the participants. The risks and benefits of study participation will be fully explained. The consent form includes information on purposes and procedures, risks and benefits, confidentiality, participant rights for participation, refusal and withdrawal, contact information, and other relevant information as required by federal regulations and our local Institutional Review Board.

Following enrollment, each study participant will be assigned a unique study identification number and their name and study ID number will be linked on the participant's Enrollment form, and in the local data management system in an encrypted file. The link is necessary in order to schedule follow-up assessments following the baseline assessment. The Locator Form, Enrollment forms, signed Consent Forms, and Contact Logs are kept in locked file cabinets in a locked office in SUNY-DMC. While in the field, participants will keep all signed consent forms on their person in a shoulder bag until they are secured at Downstate. All study participant data will be identified only by study ID numbers. A study investigator will review all of these forms at the time of enrollment and throughout each participant's time in the study and will ensure that consent forms are signed and dated by the participant and the research assistant responsible for overseeing the consent process. Due to the sensitive nature of some of the questions asked in the interviews it is possible that any breach of confidentiality could result in stigma or damage to reputations. The investigators will take numerous steps to minimize the possibility of breaches of confidentiality. We will ensure that data collection efforts take place in as private an area as possible. For quantitative interviews, participants will listen to questions via headphones, and computer screens used with A-CASI will not be visible to other study personnel, participants, or bystanders. Each study participant will be assigned a unique study identification number and their name and study ID number will be linked on the participant's Locator Form, in the Enrollment form, and in the local data management system in an encrypted file. The Locator Form, Enrollment forms, signed Consent Forms, and Contact Logs are kept in locked file cabinets in a locked office in SUNY-DMC. All study participant data will be identified by study ID numbers only. For all phases of the study, a number of steps will be taken to ensure participant confidentiality. Specifically, we will: (1) keep all files in locked offices, (2) use only code numbers to identify this information and remove all identifiers on patient records, (3) keep the key that links numbers to names in a locked file, and (4) obtain informed consent from each study participant. All study procedures will adhere to federal guidelines regarding patient confidentiality. Study participants' Identifiable Health Information (IIHI) will be retained/available for reporting until January 2022; five years after the end of the study, and may be shared with the following persons or agencies for purposes related to the conduct of the research: 1) The

sponsor(s) of the study: The National Institute of Health (NIH); 2) The Institutional Review Board of SUNY Downstate Medical Center and the applicable DMC officials and staff who supervise the way research is done and run the business operations; 3) The research team for this study; and 4) The collaborating research agency, namely Arthur Ashe Institute for Urban Health.

The locator form, contact log, and enrollment form will be kept until the evaluation is completed, after which time they will be destroyed. At that time, we will also electronically shred the computer file linking the names and ID numbers. Laptop computers used to collect ACASI data will be protected during transport through the use of locked padded cases which will remain with the interviewers at all times. Data collection will occur in the barbershop; follow-up evaluations may also take place within a private space at SUNY Downstate. In summary, this is a low risk study, conducted in an area of elevated HIV risk. All participants, whether assigned to the intervention and control will receive some health education, but the question of the effectiveness of the intervention program on reducing sexual risk behavior is not known. Based on program elements, it is our hypothesis that the program will produce changes in skills and motivation for safer sex, in community and personal empowerment, and in interpersonal communication skills, but similarly this cannot be guaranteed.

References

Albarracin, D., J. C. Gillette, et al. (2005). "A test of major assumptions about behavior change: a comprehensive look at the effects of passive and active HIV-prevention interventions since the beginning of the epidemic." *Psychol Bull* **131**(6): 856-97.

Carey, M. P. and K. E. Schroder (2002). "Development and psychometric evaluation of the brief HIV Knowledge Questionnaire." *AIDS Educ Prev* **14**(2): 172-82.

CDC. (2011). "Diagnoses of HIV Infection and AIDS in the United States and Dependent Areas, 2009." *HIV/AIDS Surveillance Report, Volume 21* Retrieved March 21, 2011, from <http://www.cdc.gov/hiv/surveillance/resources/reports/2009report/>.

CDC. (2011). "HIV in the United States." Retrieved March 23, 2011, from <http://www.cdc.gov/hiv/resources/factsheets/us.htm>.

Darrow, W. W., J. E. Montanea, et al. (2009). "AIDS-related stigma among Black and Hispanic young adults." *AIDS Behav* **13**(6): 1178-88.

